2.2.1. Clinical Overview

As of September 2021, a total of 32 participants were enrolled from 2 to 10 years old. 14 participants were randomized to 1 mg/kg once weekly (QW) arm and 15 participants were randomized to 2 mg/kg twice weekly (BIW) dosing arm and 3 participants were randomized to 1.5 mg/kg daily (QD). A total of 36 treatment related AEs were reported from 13 out of 32 participants; 3 at low dose, 8 at medium dose and 2 at high dose. The most frequently reported AEs were ISRs such as redness/rash/erythema/pruritis at the injection site. All AEs were mild or moderate in severity and there were no serious adverse events. There were no other clinically significant laboratory abnormalities or physical examination/vital sign changes. Following, administration of study drug, observed serum recifercept concentrations at all three doses were in the range of the predicted exposures in 2 to <10 year old children with achondroplasia using the population PK (PopPK) model.

In the recifercept Phase 1 study (C4181002), healthy participants were administered single (n=30) and multiple (n=24) SC doses of recifercept. In addition, 18 participants received placebo in the study. The dose-range studied in single ascending dose (SAD) part of the study was 0.3 – 20 mg/kg and in the multiple ascending dose (MAD) part was 1 mg/kg and 3 mg/kg twice weekly and 3 and 10 mg/kg once weekly for four weeks. Signs and symptoms of an injection site/infusion site reaction, including erythema, swelling, pain, inflammation, and pruritis, were the most frequently reported adverse events in the SAD and MAD part of

the study. There were no clinically significant changes in laboratory tests, vital signs or ECG. No systemic allergic reactions or serious adverse events occurred during the study.

In the SAD portion of the study, all participants were ADA negative (ADA-) prior to treatment with reciferecept. A confirmed ADA positive (ADA+) response was observed in 8 participants receiving reciferecept and 1 placebo participant at the end of the study (Day 29). In the MAD portion of the study, 2 participants were ADA+ prior to treatment with reciferecept. The majority of the participants who received multiple doses of reciferecept were ADA+ (21/24) and 2 placebo participants during the observation period.

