4. STUDY DESIGN

4.1. Overall Design

This is a phase 2 randomized, 3 arm (3 active doses of Recifercept), parallel group dose- finding study of safety, tolerability, PK and efficacy.

The study will enroll approximately 54 children with achondroplasia aged 2-10 years (inclusive) who will be enrolled and randomized to receive one of three doses of reciferecept (1 mg/kg once-weekly, 2 mg/kg twice-weekly or 1.5 mg/kg once-daily, n=18 per dose) such that approximately 45 participants are evaluable (up to 15 participants per dose). Additionally, **CCI** cohort of approximately 9 children with achondroplasia, ages 3 months to 2 years, will be enrolled later in the study (n=3 per dose). All 63 participants in this part of the study will receive reciferecept for 12 months.

PK Study Cohort:

At selected sites only, an additional PK cohort has been added to evaluate the PK of two reciferecept formulations. A total of 12 children with achondroplasia aged 2- < 11 years will be enrolled in the PK cohort (6 in each treatment sequence). Each participant will receive 2 treatments (3 mg/kg Phase 2 formulation [process 1c] and 3 mg/kg Phase 3 formulation [process 2]) in a randomized manner according to one of two sequences as outlined in [Table 1](#) below. Dose of the cohort could be changed due to emerging safety and efficacy data in the study.

PK samples collected following each dose will be analyzed to evaluate the exposures of two formulations.

Table 1. Treatment Sequence

Sequence	Period 1	Period 2
1 (n = 6)	Phase 2 study (process 1c) Formulation	Phase 3 study (process 2) Formulation
2 (n = 6)	Phase 3 study (process 2) Formulation	Phase 2 study (process 1c) Formulation

All participants who complete the study and in the opinion of the investigator, continue to have a positive risk: benefit profile, will be offered to enroll into an open-label extension (OLE) study. Participants will continue to receive recifercept at the dose previously received in this phase 2 study or at the therapeutic dose once this is identified.

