Multiple changes have been made in the manufacturing process of the drug product (process 2) which will be used in Phase 3. These changes include, but are not limited to, host cell line change, manufacturing process optimization, scale up and manufacturing site changes. Therefore, an additional PK cohort (at selected sites only) has been added, to evaluate the PK of Phase 2 formulation (process 1c) and Phase 3 formulation (process 2).

Serum & Plasma biomarker samples will be taken during the study as indicated in the [SoA](#). Further details can be found in [Section 8.7](#).

[figure not shown]

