9.2. Sample Size Determination

Sample size determination is based on the co-primary endpoint of height growth, defined as change from baseline of height at 12 months for participants on drug versus change from baseline of height at 12 months for a reference achondroplasia population. A total of 54 participants randomized to three dose levels in order to obtain 15 participants per dose, assuming a one-sided family-wise error rate of 0.05 with a Bonferroni correction (0.017 after Bonferroni adjustment for 3 comparisons), and inter-participant variability of .15 (estimated from C4181001), there is over 90% power to detect at least one dose providing 50% height growth above reference. No statistical comparison will be made between recifercept doses.

PK Study Cohort:

No formal sample size calculation was performed and 12 participants will be selected empirically to characterize PK, safety and tolerability after single 3 mg/kg dose administration of two formulations.

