The serum PK parameters for recifercept will be summarized descriptively by formulation. Serum concentrations will be listed and summarized descriptively by formulation and nominal PK sampling time. Individual participant summary profiles (mean and median plots) of the serum-concentration time data will be plotted by formulation and PK sampling time. For summary statistics and summary plots, the nominal PK sampling time will be used. For individual participant plots, the actual PK sampling time will be used, whilst the pre-dose will be set to zero. Summary plots will be presented on both linear-linear and log-linear scales.

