6.1.2. PK Cohort

Blood samples for PK analysis of Intact and total recifercept will be taken according to the Schedule of Activities given in the protocol.

The following PK parameters will be calculated for intact and total recifercept from the concentration-time values using standard non-compartmental methods:

Table 2 Non-compartmental PK Parameters

Parameter	Analysis Scale	Recifercept
C_{\max}	ln	D
T_{\max}	U	D

$t_{1/2}^*$	U	D
AUC_{inf}^*	ln	D
AUC_{168}^*	ln	D
AUC_{360}^*	ln	D

Key: A=analyzed using statistical model, D=displayed with descriptive statistics,
ln=natural-log transformed, U=raw (untransformed), *=if data permits.

To assess the pharmacokinetics of intact and total recifercept, the PKP parameters detailed above will be listed and summarized for subjects in the PK analysis set (as defined in [Section 4](#)). Missing values will be handled as detailed in [Section 5.3.1](#). Each PK parameter for intact and total recifercept will be summarized by dose. Each summary will include the set of summary statistics as specified in [Table 3](#).

Table 3 PK Parameters to be Summarized Descriptively

Parameter	Summary Statistics
AUC_{360} , AUC_{inf} , AUC_{168} , C_{max}	N, arithmetic mean, median, cv%, standard deviation, minimum, maximum, geometric mean and geometric cv%.
T_{max}	N, median, minimum, maximum.
$t_{1/2}$	N, arithmetic mean, median, cv%, standard deviation, minimum, maximum.

There will be a summary table each for Intact and Total Recifercept presenting all PK parameters. Each summary table will be grouped by dose.

To assess the relationship between the PK parameters and dose, dose normalized AUC_{tau} and C_{max} will be plotted against dose (using a logarithmic scale), and will include individual subject values and the geometric means for each dose separately. Geometric means will have a different symbol than the individual values. The values will be dose normalized (to a 1 mg/kg dose) by dividing the individual values and raw geometric means by dose. A footnote will be added to the plots to indicate that geometric means are presented.

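### The two-formulation PK cohort is a randomised crossover, but no within-child formulation ratio with an interval and no PK parameter summary by period or sequence is planned, and the SAP's by-dose tables would pool the two formulations.

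*Protocol*

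**What the plan says.** **Design.** Protocol 4.1 and its Table 1 set out a two-sequence crossover with six children per sequence. Each child receives both formulations at the same nominal dose, 3 mg/kg, which the protocol calls tentative. The Period 2 dose is on Day 29. Protocol 4.2 gives the reason: changes of host cell line, process, scale and site ahead of Phase 3. Protocol 4.1 states that "PK samples collected following each dose will be analyzed to evaluate the exposures of two formulations". On size, Protocol 9.2 says "No formal sample size calculation was performed and 12 participants will be selected empirically to characterize PK, safety and tolerability".

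**Analysis of PK parameters.** Protocol 9.4.2: "The serum PK parameters for recifercept will be summarized descriptively by formulation". SAP 6.1.2, Table 2, has the key "A=analyzed using statistical model, D=displayed with descriptive statistics". All six parameters carry D and none carries A, although Cmax and the three AUCs are already assigned a natural-log analysis scale. SAP 6.1.2 lists individual parameters and groups the summary tables by dose.

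**Antibodies.** The PK cohort schedule takes immunogenicity samples before the Day 1 dose, before the Day 29 dose and at Day 57. SAP 6.2.13 reports ADA and NAb percentages by dose and cohort. The effect of ADA on PK is optional. It may include profile plots, and concentration tables at visit and time, by antibody status and cohort. On the Phase 1 single-dose part, Protocol 2.2.1 reports: "A confirmed ADA positive (ADA+) response was observed in 8 participants receiving reciferecept and 1 placebo participant".

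**The concern.** The point of a crossover is that each child is his or her own control. Two columns of descriptives by formulation leave that unused: each column's SD mixes differences between children with variation within a child, and nothing in the table says how precisely the formulations have been compared. If tables follow the SAP's by-dose grouping, there is no formulation contrast at all.

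The second issue is Period 2. Antibodies raised by the first formulation may be present when the second is given, and no planned parameter summary separates the periods or sequences. The cohort is meant to inform the move to process 2 material, so at stake is whether an exposure difference can be read with a stated uncertainty, and whether an antibody effect could be mistaken for a formulation effect.

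**Working it through.** The plan gives no power, margin or CV for this cohort, so there is no figure of its own to reproduce. The checks below size the consequences.

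**1. What the tables can show.**
- Protocol 9.4.2: columns by formulation. SAP 6.1.2: columns by dose. With one dose for both formulations, the SAP's grouping gives one pooled column. The two passages conflict.
- With complete pairs, the difference of the two mean logs equals the mean of the within-child log differences. The ratio of by-formulation geometric means is then exactly the geometric mean within-child ratio.
- The variance of that mean difference is (s1² + s2² − 2·cov)/12. The columns give s1 and s2 but not the covariance, so the precision does not follow from them.
- Complete pairs are not guaranteed. The PK Study Cohort set (Protocol 9.3, SAP 4) needs a dose of each formulation but only one evaluable concentration. The parameter set needs only one parameter, and the AUCs are conditional on the data.

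**2. Precision of a paired analysis.** Within-child CV is an assumption; the documents give none. Error df = 24 observations − 1 − 11 (children) − 1 (period) − 1 (formulation) = 10. The 90% interval factor is exp[t(0.95, 10) × s_w × √(2/12)], with s_w = √ln(1 + CV²) and t × √(2/12) = 1.812 × 0.408 = 0.740.

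| Within-child CV | s_w | 90% CI at a true ratio of 1 |
|---|---|---|
| 20% | 0.198 | 0.86-1.16 |
| 30% | 0.294 | 0.80-1.24 |
| 40% | 0.385 | 0.75-1.33 |
| 50% | 0.472 | 0.71-1.42 |

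**3. Drug washout.** Day 1 to Day 29 is 28 × 24 = 672 h. The adult mean half-lives used here are 47.8 h and 97.4 h (Protocol 2.2.1). 672/97.4 = 6.9 and 672/47.8 = 14.1 half-lives, leaving 2^(−6.9) = 0.84% down to 0.006% of Period 1 drug. Carry-over of drug is small if children resemble adults.

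**4. Antibodies at the Day 29 dose.** The rate is 8 of the 30 single-dose recipients in Phase 1 = 26.7% (exact 95% CI 12.3-45.9%). Expected in 12 children: 12 × 0.267 = 3.2 (1.5 to 5.5). Chance of at least one: 1 − (22/30)^12 = 97.6%. Applying an adult rate to children is an assumption.

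**5. When this biases the formulation ratio.** Let d be a common Period 2 effect on the log scale, n1 the completers given process 1c first and n2 those given process 2 first. The unadjusted by-formulation log ratio shifts by d(n1 − n2)/(n1 + n2).
- 6/6 completers: no shift.
- Period 2 exposure halved (assumption): 6/5 gives 0.5^(1/11) = 0.94; 6/4 gives 0.5^(2/10) = 0.87.
- Formulation-specific case (assumption): only process 2 raises antibodies, in 26.7%, halving later exposure in those children. The ratio is multiplied by exp(−0.5 × 0.267 × ln 0.5) = 1.10, even with 6/6.

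A period term removes the common effect whatever the completion pattern. It does not remove the formulation-specific one.

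**The case against.** The strongest reply is that the aim is openly descriptive. The objective is to evaluate PK, twelve children were chosen without a calculation, and no margin or hypothesis is stated. That stands: this is a missed use of the design, not a failed comparability test.

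Four stronger readings are tempting, and the documents do not support them.

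- **That no formulation ratio can be obtained.** It can, from complete pairs in by-formulation tables or from the listed individual values. What is absent is a planned ratio with its interval. Anyone computing one from the listings would be choosing the method after seeing the data.
- **That the cohort cannot reveal antibody carry-over.** The Day 29 pre-dose sample is scheduled, and SAP 6.2.13 permits concentration tables by visit and antibody status. Period 2 has its own visit numbers, so such a table would separate the periods. The gap is that this output is optional and has no formulation or sequence split.
- **That antibodies will distort Period 2.** The 97.6% is the chance of at least one positive child, not of altered PK. Neither document reports that ADA changes clearance. In the multiple-dose part 21 of 24 became positive, yet accumulation ratios were all above 1 and half-lives were 71.3 to 97.4 h.
- **That ignoring the pairing widens the interval by a stated multiple.** Any such figure needs two assumed CVs and an unpaired interval that nobody plans to report.

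It can also be said that the samples feed the population PK model (Protocol 8.5, SAP 6.2.12), which could carry formulation as a covariate. Its modelling plan is a separate document, and nothing in the protocol or SAP states a formulation, period or sequence term. This leaves the gap open.

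**Conclusion.** The point holds in this limited form. A randomised crossover is planned without a within-child ratio and interval, without parameter summaries by period or sequence, and with SAP tables whose grouping conflicts with the protocol and would merge the two formulations.

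The lost information is the precision of the comparison: roughly 0.86-1.16 at a within-child CV of 20%, widening to 0.71-1.42 at 50%, assuming twelve complete pairs. The antibody question is secondary. About 3 of 12 children (1.5 to 5.5) could be positive at the second dose if adult rates apply, and the contrast is biased only if completion is unequal between sequences or the formulations differ in immunogenicity. A host cell line change makes the latter worth looking at, but the documents give no evidence that it occurs. The change should be made because it is nearly free and serves the cohort's primary objective.

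**What to change.** 1. Reconcile SAP 6.1.2 with Protocol 9.4.2 so that PK parameters are tabulated by formulation and period, and state for each parameter how many children contribute both periods.
2. In SAP Table 2, code Cmax, AUC168, AUC360 and AUCinf as A. Fit a ln-scale mixed model with sequence, period and formulation as fixed effects and child as a random effect.
3. Report the process 2 / process 1c geometric mean ratio with a 90% CI for intact and total recifercept, as estimation only, with no equivalence claim.
4. Present Period 2 PK by Day 29 pre-dose ADA status, descriptively. Do not exclude positive children from the ratio: their status arises after randomisation and may depend on the first formulation.
5. Add the Period 1-only ratio, labelled supportive. It is free of carry-over but compares 6 with 6. With assumed log-SDs of 0.20 within and 0.40 between children, its 90% interval at a ratio of 1 is exp[±1.812 × √(0.20² + 0.40²) × √(2/6)] = 0.63-1.60.

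**Cost.** SAP wording and a small number of tables: 4 parameters × 2 analytes = 8 main ratios, plus 8 supportive ones. No new samples, visits or children.

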9.4.3. Secondary Endpoint(s)

The secondary efficacy endpoint of change from baseline of the difference of arm span to height difference at 12 months will be analyzed using an analysis of variance (ANOVA) model comprising terms for recifercept dose groups. Change from baseline estimates for height and their corresponding 80% confidence intervals will be provided via least-square means. The population for the primary analysis will be based on the FAS, while the PPAS is the population that will be used for sensitivity analysis.

Additional safety endpoints (laboratory values, physical examination, vital signs and immunogenicity) will be analyzed as change from baseline by dose group.

PK Study Cohort:

The safety data will be summarized in accordance with Pfizer Data Standards. All participants who receive IP (safety population) will be included in the safety analyses. All safety data will be summarized descriptively through appropriate data tabulations.

CCI

9.4.5. Other Safety Analyses

All safety analyses will be performed on the safety population.

9.4.6. Other Analyse(s)

Patient-reported/observer-reported outcome assessments will be summarized by dose. Additional analysis of these assessments will be detailed in the SAP or in a separate analysis plan.

Pharmacogenomic or biomarker data from Banked Biospecimens may be collected during or after the trial and retained for future analyses; the results of such analyses are not planned to be included in the CSR.

9.4.7. Pharmacokinetic Data

Nonlinear mixed effect modeling will be performed to evaluate pharmacokinetic parameters including clearance, area under the curve at steady state over the dosing interval for reciferecept. PK will be assessed on an ongoing basis using a sparse sampling approach to inform and update the PopPK model. The PK data from Block A participants aged ≥ 6 to < 11 years will be integrated into the PopPK model developed using healthy adult PK data, to confirm the dosing recommendations in younger age sub-cohorts (≥ 2 to < 6 years and ≥ 3 months - < 2 years).

PK Study Cohort:

Non-compartmental analysis will be conducted to evaluate the PK of the two formulations administered in the PK study cohort.

9.5. Interim Analyses

Interim analyses may be performed to assess efficacy and safety after approximately 45 participants (up to 15 per dose), complete their study participation through 50% of the study (completion of 6 months treatment). Before any interim analysis is instigated, the details of the objectives, decision criteria, dissemination plan, and method of maintaining the study blind as per Pfizer's SOPs will be documented and approved in a charter. In addition, the analysis details must be documented and approved in an interim analysis SAP or final SAP.

The Bonferroni correction method is used to control the overall familywise error rate of 0.05 for multiple comparisons. The post-baseline estimate will be considered statistically significant at the 1-sided 0.017 level. No statistical comparisons will be performed between treatment arms.

9.6. Data Monitoring Committee or Other Independent Oversight Committee

This study will use an eDMC. The eDMC is independent of the study team and includes only external members. The eDMC charter describes the role of the eDMC in more detail.

The eDMC will be responsible for ongoing monitoring of the safety of participants in the study according to the charters. The recommendations made by the eDMC to alter the conduct of the study will be forwarded to the appropriate Pfizer personnel for final decision. Pfizer will forward such decisions, which may include summaries of aggregate analyses of safety data to regulatory authorities, as appropriate.

[figure not shown]
The study team will meet to assess progression to the next enrollment block ([Section 1.2](#)) based on the available safety and PK data. If safety signals are identified at this review (see [Section 6.1](#)) then a meeting of the eDMC will be convened to decide next steps.

The eDMC will meet regularly to assess all available safety and PK data to ensure ongoing safety of all trial participants. The eDMC will review unblinded safety data in order to fully assess the impact of dose/exposure on safety signals. A patient advocate will also be included on the eDMC if an appropriately qualified individual can be identified as agreed upon by the eDMC chairperson.

10. SUPPORTING DOCUMENTATION AND OPERATIONAL CONSIDERATIONS

10.1. Appendix 1: Regulatory, Ethical, and Study Oversight Considerations

CCI

The protocol, protocol amendments, ICD, SRSD(s), and other relevant documents (eg, advertisements) must be reviewed and approved by the sponsor and submitted to an IRB/EC by the investigator and reviewed and approved by the IRB/EC before the study is initiated.

Any amendments to the protocol will require IRB/EC approval before implementation of changes made to the study design, except for changes necessary to eliminate an immediate hazard to study participants.

The investigator will be responsible for the following:

- Providing written summaries of the status of the study to the IRB/EC annually or more frequently in accordance with the requirements, policies, and procedures established by the IRB/EC;
- Notifying the IRB/EC of SAEs or other significant safety findings as required by IRB/EC procedures;
- Providing oversight of the conduct of the study at the site and adherence to requirements of 21 CFR, ICH guidelines, the IRB/EC, European regulation 536/2014 for clinical studies (if applicable), and all other applicable local regulations.

10.1.1.1. Reporting of Safety Issues and Serious Breaches of the Protocol or ICH GCP

In the event of any prohibition or restriction imposed (ie, clinical hold) by an applicable regulatory authority in any area of the world, or if the investigator is aware of any new information that might influence the evaluation of the benefits and risks of the study intervention, Pfizer should be informed immediately.

In addition, the investigator will inform Pfizer immediately of any urgent safety measures taken by the investigator to protect the study participants against any immediate hazard, and of any serious breaches of this protocol or of ICH GCP that the investigator becomes aware of.

